9.1 Definition of Baseline and Change from Baseline

The Baseline is defined as the MAGNIFY MS Baseline (parent study Baseline) that is specified in Section 9 of MAGNIFY MS IAP version 3.0, unless otherwise specified.

Absolute and percent changes from baseline are defined as:

- Absolute change = Visit value Baseline value
- Percent change = 100 * (Visit value Baseline value) / Baseline value

The Percentage Change from Baseline will be set to missing for participants with a zero at Baseline.

All changes that are defined as comparing to prior initial dose of cladribine tablets will use the MAGNIFY MS Baseline as reference.

9.2 Definition of Visit Dates

The visit start date is the date of the first assessment which belongs to the corresponding visit.

The visit end date is the date of the last assessment which belongs to the corresponding visit.

9.3 Definition of Duration

Durations in days will be calculated by the difference of start and stop date + 1 if not otherwise specified.

9.4 Conversion Factors

The following conversion factors will be used to convert days into months or years for all observations except Visit related dates:

- 1 month = 30.4375 days,
- 1 year = 365.25 days.

9.5 Time Window

- Day 1 is the day of start of study medication at MAGNIFY MS Baseline Visit, the day before is Day -1 (no Day 0 is defined).
- Study day is defined relative to Day 1.

The visit schedule in the Extension Study is defined as follows:

- 1 month = 30 days,
- 1 year = 360 days,

relative to the M24 Visit in the parent study.

- MAGNIFY Extension Baseline Visit: The visit is planned to coincide with or be as near to M24 as possible to minimize the transition gap period, it may also be the same visit as M24.
- Visit 1: 1 year ((360 days) after M24 Visit (\pm 30 days)
- Visit 2: 2 years (720 days) after M24 Visit (± 30 days)

Visit 1 and Visit 2 will also be referred to as the M36 Visit and the M48 Visit, respectively, in the following sections of this IAP as well as in the Tables, Listings, and Figures (TLF) outputs, for consistent presentation of analyses and results over time. Footnotes will be added in the TLF outputs to clarify that these Visits are to be understood as nominal Visits.

In each analysis, should an assessment be delayed, participants' assessment data will be treated as though it occurred at the nominal time point specified (i.e., data collected out of visit windows will not be excluded or adjusted in any analysis) and inferences will be conducted accordingly. Thus, further time windows will not be specified. The MRI assessment will be the only exception to this rule. Handling of out-of-window MRI assessments is discussed in Section 9.8.

All observations from unscheduled visits will be included only in the analyses of visit independent summaries (e.g., counts of AEs, concomitant medications and procedures, relapse reporting and EDSS) unless for the last assessment available. In this case the missing Early Withdrawal (EW) visit will be imputed by the unscheduled visit.

The assessments of the EW visit will be mapped to the nearest planned post-baseline visit with a missing assessment before or after the EW visit of the individual assessment for all statistical analyses and descriptive summaries. As not all assessments of the EW are performed at each visit, the different assessments of the EW can be assigned to different visits. If the duration (in days) between the EW visits and two missing planned visits are equal, then the assessment will be assigned to the later visit.

9.6 Study Period

Study Periods

The following study periods are defined:

Treatment Period (i.e., Parent Study Period): see MAGNIFY MS IAP version 3.0 for definition.

Course 1 Treatment Period: see MAGNIFY MS IAP version 3.0 for definition.

Course 2 Treatment Period: see MAGNIFY MS IAP version 3.0 for definition.

Gap Period:

- Start = Visit end date of M24 Visit + 1
- End = Extension Study Baseline Visit start date

Year 3 Visit Period:

- Start = Visit end date of M24 Visit + 1
- End = Visit end date of M36 Visit

Year 4 Visit Period:

- Start = Visit end date of M36 Visit + 1
- End = Visit end date of M48 Visit

Year 3 Visit and Year 4 Visit Period (i.e., **Extension Study Period**):

- Start = Visit end date of M24 Visit + 1
- End = Visit end date of M48 Visit

After start of study medication until end of Year 3 Visit Period:

- Start = Start of study medication (see MAGNIFY MS IAP version 3.0 for definition)
- End = Visit end date of M36 Visit

After start of study medication until end of Year 4 Visit Period (i.e., **Parent and Extension Study Period**):

- Start = Start of study medication (see MAGNIFY MS IAP version 3.0 for definition)
- End = Visit end date of M48 Visit

In case of missing M48 Visit or early discontinuation before an End of Period defined above, the Visit end date of EW Visit will be used to replace the corresponding End date, or the study discontinuation date will be used if the EW visit was not performed.

In case of missing M36 Visit, the Visit end date of M36 Visit in the above definitions (including Start and End) will be replaced by MAGNIFY MS M24 Visit date + 480 days (which is obtained by 360 (12 months) + 90 (3 months delay allowed for FAS) + 30 (Visit window)), or the Visit end date of EW Visit if earlier, or date of discontinuation if earlier and the EW Visit was not performed.

Study Periods for MRI Assessments

The MRI scans in the parent study were reconciled during central MRI review process. Therefore, MRIs were considered as Baseline MRIs if assigned to the Baseline Visit by the central imaging review.

The following study periods for MRI assessments are defined as per MAGNIFY MS IAP version 3.0 with extension to Month 36 Visit and Month 48 Visit MRI scans:

Baseline Period (p₀): The Baseline Period is defined as the Period between the Screening and the Baseline MRI scan in MAGNIFY MS trial.

Post-Baseline Periods (ppost-Baseline):

Yearly Periods:

Period 12.1 (p_{12.1}) is defined as the Period between Baseline to Month 12 MRI scans,

Period 12.2 (p_{12.2}) is defined as the Period between Month 12 to Month 24 MRI scans,

Period 12.3 (p_{12.3}) is defined as the Period between Month 24 to Month 36 MRI scans,

Period 12.4 (p_{12.4}) is defined as the Period between Month 36 to Month 48 MRI scans.

2-Year Period:

Period 24.1 (p_{24.1}) is defined as the Period between Baseline to Month 24 MRI scans.

3-Year Period:

Period 36.1 (p_{36.1}) is defined as the Period between Baseline to Month 36 MRI scans.

4-Year Period:

Period 48.1 (p_{48.1}) is defined as the Period between Baseline to Month 48 MRI scans.

Sequential Visit Periods:

For p_{100.0}, p_{100.1}, p_{100.2}, p_{100.3}, p_{100.6}, p_{100.12}, p_{100.15}, p_{100.18}, p_{100.24}, see Section 9 of MAGNIFY MS IAP version 3.0.

Period 100.36 ($p_{100.36}$) is defined as the Period between Month 24 to Month 36 (equivalent to $p_{12.3}$) MRI scans.

Period 100.48 ($p_{100.48}$) is defined as the Period between Month 36 to Month 48 (equivalent to $p_{12.4}$) MRI scans.

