6.1.1 Cut-off Date

Only data up to and including Visit 1 of each participant will be analyzed in the IA. Therefore, the cut-off date is defined as the maximum Visit 1 date (i.e., date of the last assessment for Visit 1). For participants with a missing Visit 1, the cut-off date will be 1 year (360 days) after end date of M24 Visit in the MAGNIFY MS trial. This includes participants of the MAGNIFY MS Extension Study who discontinued before Visit 1.

Cut-off date (Visit 1 done) = Visit 1 end date (i.e., Maximum Visit 1 date)

Cut-off date (Visit 1 not done) = 1 year (360 days) after end date of M24 Visit in the MAGNIFY MS trial

Any assessments from later than Visit 1 will not be included in the IA, however, any events or concomitant medications reported during these visits that have an onset/start date before or at the cut-off date will be included.

All data included in the IA will undergo a data cleaning process, however, as no decisions on further study conduct are based on this IA, it is not required to have all data 100% cleaned.

Details and level of data cleaning will be documented in data management plans. The quality of the data will be reviewed during the Data Review Meeting.

^{**} Ongoing SAEs and events of lymphopenia (also if not serious) with an onset date prior to the parent study exit date will be recorded as medical history in the extension study.

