8.1 Definition of Analysis Sets

Enrolled Set (ES)

All participants who provided informed consent.

Full Analysis Set (FAS)

The FAS will include all enrolled, eligible participants.

Safety Analysis Population (SAF)

All participants treated with at least one dose of cladribine tablets during the parent study.

Treatment Completer Set (TCS)

All participants from the FAS who completed the full treatment course of the first and second year in the parent study (i.e., participants who were in TCS-2 as defined in MAGNIFY MS IAP version 3.0).

Analyses per Analysis Set

Unless otherwise specified, all efficacy analyses will be performed on the FAS and all safety analyses will be performed on the SAF. The primary analysis will also be repeated on the TCS as a sensitivity analysis.

If not stated otherwise, disposition of participants will be summarized on the ES, previous and concomitant medications will be summarized on the FAS, and the analyses on demographics and other baseline characteristics will be based on the FAS.

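### For a missed M36 visit, SAP 9.6 sets the Year 3/Year 4 boundary at day 480 through an undefined 90-day allowance, while SAP 6.1.1 stops the interim Year 3 data at day 360

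*SAP*

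**What the plan says.** SAP 9.6 uses the end date of the M36 Visit both to close the Year 3 Visit Period and, one day later, to open the Year 4 Visit Period. If M36 is missing, that date is replaced wherever it appears by "MAGNIFY MS M24 Visit date + 480 days (which is obtained by 360 (12 months) + 90 (3 months delay allowed for FAS", and a 30-day visit window completes the sum. A cap applies: "or the Visit end date of EW Visit if earlier, or date of discontinuation if earlier and the EW Visit was not performed". The full 480 days therefore concern only participants who miss M36 and continue.

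Four other places bear on this:

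- **SAP 6.1.1 (interim cut-off):** "For participants with a missing Visit 1, the cut-off date will be 1 year (360 days) after end date of M24 Visit".
- **SAP 8.1 (analysis sets):** "The FAS will include all enrolled, eligible participants". Protocol 9.3 defines the FAS in the same way, and the list of FAS exclusion reasons in SAP 10.2.2 contains only eligibility criteria.
- **SAP 9.5 (visit schedule):** "Visit 1: 1 year ((360 days) after M24 Visit" and "Visit 2: 2 years (720 days) after M24 Visit", each with a window of ± 30 days. Late assessments stay in the analysis as if on time, MRI excepted, and no further windows are to be set. Protocol 4.1 also makes ± 30 days the maximum.
- **SAP 14.2.1 (secondary NEDA-3):** the Year 4 clock starts the day after the M36 end date. Year 3 censoring is the earliest of the last MRI in the period, the last EDSS in the period and the period end.

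**The concern.** The boundary between two reported periods rests on a constant whose largest added term has no source in the documents. The 90 days are attributed to the FAS, but no FAS definition supplied here mentions visit delay. The interim rule for the same missed visit uses a different number.

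Three things follow for a participant who misses M36 and attends M48:

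1. Year 3 and Year 4 become very unequal in length.
2. Clinical events in the third of a year after nominal M36 are credited to Year 3.
3. Year 3 NEDA-3, which SAP 6.1 reports at the interim and SAP 14.2.1 at the final analysis, covers different stretches of follow-up.

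The secondary Year 3 and Year 4 NEDA-3 analyses, the cumulative analysis from first dose to the end of Year 3, and the related subset analyses are at stake.

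**Working it through.** **Inputs.** Substitute boundary: 480 days (SAP 9.6). Nominal M36: day 360 ± 30, and nominal M48: day 720 ± 30 (SAP 9.5). Interim cut-off without Visit 1: day 360 (SAP 6.1.1). Time to event in months: (event or censoring date − start date + 1)/30.4375 (SAP 14.1.1 and 14.2.1). Days are counted from the M24 Visit. SAP 9.6 anchors on the M24 Visit date and 6.1.1 on its end date, a small mismatch ignored here.

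**Step 1: reproduce the plan's figure.** 360 + 90 + 30 = 480, as stated. The 90-day term matches the schedule convention "1 month = 30 days" (3 × 30), but its origin is not given.

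**Step 2: distance from the other rules.** 480 − 360 = 120 days beyond the interim rule. 480 − 390 = 90 days beyond the upper edge of the Visit 1 window.

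**Step 3: period lengths when M36 is missed and M48 attended.**

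- Year 3: 480 days; 480/30.4375 = 15.8 months, as a maximum.
- Year 4, starting on day 481:
  - M48 on day 690: 210 days, 6.9 months
  - M48 on day 720: 240 days, 7.9 months
  - M48 on day 750: 270 days, 8.9 months

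An attender with M36 on day 360 and M48 on day 720 has 720 − 361 + 1 = 360 days in Year 4, or 360/30.4375 = 11.8 months. The ratio 240/360 = 0.67 means about one third less Year 4 exposure.

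**Step 4: alternative constants, M48 on day 720.**

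| Boundary | Year 3 | Year 4 |
|---|---|---|
| Day 360 | 360 days | 360 days |
| Day 390 | 390 days | 330 days |
| Day 480 | 480 days | 240 days |

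**Step 5: which events move.** A first relapse on day 400 falls in Year 4 under a 360-day boundary and in Year 3 under 480. An EDSS worsening at an unscheduled visit on that day, later confirmed, moves in the same way. At the interim the day-400 relapse lies beyond the cut-off and is absent from Year 3; at the final analysis it is a Year 3 event. The M48 scan falls in Year 4 under all three constants, so scheduled MRI findings do not move.

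**Step 6: what the span means, as an illustration only.** Assume a constant hazard and an event-free probability of 0.70, 0.80 or 0.90 per 360 days. Over 480 days it becomes 0.62, 0.74 or 0.87 (p to the power 480/360). Over 240 days it becomes 0.79, 0.86 or 0.93 (p to the power 240/360). This describes the affected participants' periods. It is not the shift in a reported Kaplan-Meier estimate.

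**Step 7: number affected.** The documents give none. If 2% to 8% of the 200 to 220 evaluable participants planned in Protocol 1.1 missed M36 and continued (an assumption), that is 0.02 × 200 = 4 to 0.08 × 220 = 17.6, or about 4 to 18 people.

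**The case against.** Several points on the other side are sound and limit the finding.

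- **Month 12 of Year 4.** A reader might infer that day 480 is what keeps these participants from the 12-month point. It is not the sole cause. A fully on-schedule attender reaches only 11.8 months, because visits follow a 360-day year while time is divided by 30.4375. With a day-360 boundary, M48 would have to fall on day 726 or later to pass month 12. Day 480 enlarges the shortfall.
- **Lost relapses.** A reader might infer that relapses between month 12 and day 480 are counted nowhere. They remain in the Year 3 curve, the primary endpoint, the cumulative NEDA-3 analyses and the relapse analyses. They are assigned to a different period, not dropped.
- **Event-free follow-up.** The 15.8 months seldom become observed event-free time. Year 3 censoring includes the last MRI, and MRI is scheduled only at Visits 1 and 2. The longer period matters mainly for relapse or EDSS events on days 361 to 480.
- **Interim versus final.** SAP 6.1.1 is a data cut-off, not a period definition, and the interim is exploratory with no decision attached. It is too strong to say that the SAP contradicts a general 360-day rule; SAP 9.5 only sets the nominal schedule on which 480 is built. What stands is that one endpoint and one missed visit have two different end points.
- **Source of the 90 days.** It may come from the parent study's analysis plan, which SAP 9.6 cites for other periods and which is not available here. So one cannot say that the allowance does not exist, only that the protocol and this SAP do not define it. SAP section 9 applies the parent plan's rules to parent-study data, and this SAP defines its own FAS.

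A need to accommodate late visits does not rescue the constant. A late M36 that took place uses its actual end date; the substitute applies only when there was no visit.

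**Conclusion.** The point holds as a correctable inconsistency in secondary analyses. For participants who miss M36 and attend M48 within its window, Year 3 is up to 480 days and Year 4 is 210 to 270 days. Relapse or EDSS events on days 361 to 480 are assigned to Year 3, and the Year 3 endpoint spans differ between interim and final analysis.

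It does not reach the primary endpoint when M48 is attended, because that period runs from the day after M24 to M48 regardless of M36. Nor do the documents support a claim that the reported secondary proportions will be materially wrong: the number affected is unknown, the 4 to 18 above rests on an assumed rate, and no change in an estimate can be calculated. The study is exploratory with no formal hypothesis test. The change is worth making because the rule is unsupported as written and cheap to correct.

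**What to change.** In SAP 9.6, define the substitute M36 date as the M24 Visit end date + 360 days, or the early-withdrawal or discontinuation date if earlier. Use it for both the Year 3 end and the Year 4 start, and delete the FAS-delay derivation. This agrees with SAP 6.1.1 and the nominal visit in 9.5, and it removes the mismatch in the M24 anchor.

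Day 360 is not the only coherent choice. If the sponsor prefers another constant, such as 390 (360 plus the 30-day window), the SAP should state its source and use the same value in 9.6 and 6.1.1. It would also help to report how many participants had the substitute date applied.

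The cost is one constant in the SAP text and in the period-derivation program, with no new data.

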5.1 Inclusion Criteria

Participants are eligible to be included in the study only if all the following criteria apply:

1. Participants of the MAGNIFY MS trial who received at least a single dose of cladribine tablets during the MAGNIFY MS trial and data on MRI is available/acquired from at least parent study Month 18 or Month 24 visit and EDSS and relapse from parent study Month 24 visit.

Informed Consent

2. Capable of giving signed informed consent, as indicated in Appendix 2, which includes compliance with the requirements and restrictions listed in the informed consent form (ICF) and this protocol.

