9.8 Data Handling for MRI data

MRI data will be integrated with MRI data from the MAGNIFY MS trial, which will be handled according to "Data Handling for MRI data – Data handling of Tertiary endpoints" in Section 9 of the MAGNIFY MS IAP version 3.0.

The MRIs will be evaluated by independent central review. The assignment of MRIs to the respective Visits in the parent study was ensured by the central reading process, while this process is not adopted in the Extension Study. Therefore, the statistical analysis will be based on the MRI Visit assignments as provided by central reading for parent study data and MRI Visit assignments as reported in the eCRF for Extension Study data. A 6-months window will be allowed for the Extension Study MRI data. An MRI assessment will be excluded from all analyses if the absolute value of (MRI assessment date – Visit date) > 185 days (which is obtained by 180 [6 months] + 5 [window allowed by protocol]).

All derived lesion counts (except for the Mean T1 Gd+ lesion count) as specified below will be classified as Not Evaluable (NE) if one of the components required for the calculation has been classified as NE by the central reading. The Mean T1 Gd+ lesion count will be set to NE only, if all T1 Gd+ lesion counts that correspond to the respective Period are classified as NE. In all other cases the mean will be calculated based on the available counts during the respective Period.

For definition of Period see Section 9.6 "Study Periods for MRI Assessments".

T1 Gd+ lesion count

- The T1 Gd+ are defined as follow: T1 Gd+ lesion count (by Visit) = T1 Gd+ lesions count from the MRI at the respective Visit.
- Mean T1 Gd+ lesion count (by Period) = sum of all T1 Gd+ lesion counts during the Period /# of scans belonging to the respective Period with non-missing T1 Gd+ lesion count.

All MRI scans belonging to a Period are MRI scans that have been performed during the Period including start and end Visits. For post-Baseline periods starting at Baseline, the Baseline Visit will not be included. For example, Period 48.1 will include all MRI scans during both MAGNIFY MS trial and Extension Study except Screening and Baseline Visit.

- New T1 Gd+ lesion count (by Period)
 - For Periods including up to Month 24 Visit, refer to "Data handling for MRI data: Data handling of Tertiary endpoints" in Section 9 of MAGNIFY MS IAP version 3.0
 - For other Periods ending at Month 36 / Month 48 Visit,

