 New T1 Gd+ lesion count = T1 Gd+ lesions count from the MRI at Month 36 / Month 48 Visit due to longer periods

For example: New T1 Gd+ lesion count of the Period between Month 24 and Month 36 (p12.3) is equal to T1 Gd+ lesion count from the MRI at Month 36 Visit.

Active T2 lesion count

As the active (i.e., the new or enlarging) T2 lesion count depends on the length of the Period, it will be presented as reported (non-standardized) and annualized (standardized to 1 years (365.25 days)):

- Period length (days) = MRI date at end of Period MRI date at start of Period +1,
- Annualized active T2 lesion count (by Period) = Total number of active T2 lesions per Period * 365.25/ Period length.

The following types of T2 lesions are defined per Period (standardized and non-standardized):

- Total new T2 lesion count =
 - Total number of new T2 lesions with T1 Gd+
 - + Total number of new T2 lesions without T1 Gd+
- Total enlarging T2 lesion count =

Total number of enlarging T2 lesions with T1 Gd+

- + Total number of enlarging T2 lesions without T1 Gd+
- Total active T2 lesion count =

Total new T2 lesion count

+ Total enlarging T2 lesion count

Note: the number of new or enlarging T2 (with and without T1 Gd+) will be provided by central reading for each of the Periods including the Sequential Visit Periods.

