9.10 Covariates and Stratification Factors

The following covariates are defined:

Unless otherwise specified, these factors will be obtained from the baseline information of the MAGNIFY MS Baseline.

Age

See MAGNIFY MS IAP version 3.0.

EDSS at Baseline

see MAGNIFY MS IAP version 3.0.

Pooled centers

Some centers will have few eligible participants only. Therefore, the centers will be pooled together by country except for

• sites that have more than 12 participants in the FAS (i.e., these sites will not be pooled with any other site).

Some countries will have few eligible participants only. Therefore, countries will be pooled as follows:

- Scandinavia = Finland and Sweden
- Mediterranean = Italy and Spain
- o France-UK = France and UK
- o Austria-Hungary-Czech = Austria, Hungary, and Czech Republic
- Australia-Canada = Australia and Canada

The following MRI specific covariate is defined:

Time between scans: in Years

Time between scans (in Years) is calculated as follows:

- Time between scans (in Years) = (MRI date of the Visit MRI of the previous Visit + 1) /365.25, i.e.:
 - If (Visit= Month 36) then Time between scans (in Years) = (MRI date at Month 36
 MRI date at Month 24 + 1)/365.25
 - If (Visit= Month 48) then Time between scans (in Years) = (MRI date at Month 48
 MRI date at Month 36 + 1)/ 365.25

If the corresponding MRI is available and the time between scans is missing (due to preceding MRI being missing) it will be replaced by expected time as follows:

- Month 36 Visit = 1 year
- Month 48 Visit = 1 year

For calculations for Month 1, 2, 3, 6, 12, 15, 18, 24 Visits, see MAGNIFY MS IAP version 3.0 Section 9.

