14.1.1 Primary Objective: Derivation and analysis of the primary endpoint

No Evidence of Disease activity (NEDA), also referred to as freedom from disease activity, is a new goal that is emerging in MS treatment. NEDA is a composite measure of disease activity, including relapses, cognition and disability progression, and MRI activity.

NEDA-3 during the Extension Study Period is defined as absence of the following three events during the Period:

- Qualifying Relapses
- 6-months Confirmed Disability Progression (6MCDP, see definition below)
- MRI Activity (i.e., presence of T1 Gd+ lesions and/or active T2 lesions)

NEDA-3 will be analyzed with the Kaplan-Meier (KM) time-to-event method to reduce the impact of unknown/missing information.

The start date will be the end date of M24 Visit + 1.

The event date will be defined as the minimum of

- the onset date of the first qualifying relapses during the Extension Study Period
- the start date of the first 6MCDP during the Extension Study Period (see definition below)
- the scan date of the first MRI during the Extension Study Period where at least one T1 Gd+ lesion or at least one active T2 lesion (see Section 9.8 for definition) is identified.

Imputation of partial onset dates of relapses is described in Section 9.7. Since full dates of MRI scan and EDSS assessment are mandatory, partial dates of 6MCDP, or MRI Activity are not expected.

If the participant did not experience any of the three events described above during the Extension Study Period, the minimum of the scan date of the last available MRI, the assessment date of the last available EDSS, and the Extension Study completion/discontinuation date will be used as the censoring date.

The time to disease activity (in months) will be calculated as [event date or censoring date as applicable – start date + 1]/30.4375. The number of participants at risk, failed, and survival rate (i.e., the proportion of participants with NEDA-3) along with the 95% CI will be estimated as per the KM method and reported at 6-months intervals. The KM survival curve will be plotted as well.

A descriptive summary of number and proportion of participants with event (overall and by type of event, i.e., qualifying relapse, 6MCDP, or MRI activity as the earliest event) and censored will be also presented.

6MCDP

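### The SAP defines no T2 comparison confined to Month 24–Month 48, yet it can censor participants without an M36 scan as NEDA-3 event-free at M48

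*SAP*

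**What the plan says.** **Periods.** SAP 9.6 lists two MRI Periods that lie wholly in the extension. Period 12.3 "is defined as the Period between Month 24 to Month 36 MRI scans" and Period 12.4 "is defined as the Period between Month 36 to Month 48 MRI scans"; Periods 100.36 and 100.48 are equivalent to these two. The only other Period ending at Month 48 is Period 48.1, which "is defined as the Period between Baseline to Month 48 MRI scans".

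**Source of the counts.** SAP 9.8 says that new and enlarging T2 counts "will be provided by central reading for each of the Periods including the Sequential Visit Periods". A derived count is not evaluable "if one of the components required for the calculation has been classified as NE by the central reading"; a scan that was never made is not addressed. T1 Gd+ at M36 or M48 is the count on that single scan and needs no earlier one. Extension scans more than 185 days from the visit date are excluded.

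**Event and censoring.** In SAP 14.1.1 the MRI event is the first extension scan showing a T1 Gd+ or active T2 lesion; the Period that supplies the T2 count is not named. Without an event, the censoring date is "the minimum of the scan date of the last available MRI", the last available EDSS date and the completion or discontinuation date.

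**Descriptive rule.** In 14.1.1, MRI activity is absent if there is at least one post-Baseline MRI and no lesion was observed. In 14.2.1, for Course 1 and Course 2, at least one available active T2 value is required as well.

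**Eligibility.** Protocol 5.1 requires that "data on MRI is available/acquired from at least parent study Month 18 or Month 24 visit", so a participant may enter without a Month 24 scan.

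**The concern.** The Kaplan-Meier method was chosen for the primary endpoint to limit the effect of missing information. That works only if follow-up stops counting when one component can no longer be assessed. Here the censoring date depends on whether a scan exists, not on whether the T2 comparison could be made. A participant without an M36 scan has no reference for Period 12.4. Unless another event is found, the M48 scan date still counts as event-free follow-up, so a comparison that was not made is treated as a finding of no lesion. At stake is the primary NEDA-3 proportion. The last-available-MRI wording also governs the NEDA-3 analyses in 14.2.1, time to first disease activity in 14.2.2 and time to first active T2 lesion in 14.2.3.

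**Working it through.** The plan states no figure on this point to reproduce, so the check follows the rules through one case and then sizes the effect.

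**1. The rules applied to one case.** Assume no usable M36 scan, an M48 scan with no Gd+ lesion, an EDSS at M48, no relapse and no 6MCDP.

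- Period 12.3 has no end scan and Period 12.4 has no start scan, so neither gives a T2 count.
- The M48 T1 Gd+ count is zero, so the MRI event rule is not met.
- Last MRI, last EDSS and completion all fall around M48, so the participant is censored there.
- Time is days/30.4375 (SAP 14.1.1), with M48 at 720 ± 30 days after M24 (SAP 9.5). 720/30.4375 = 23.7 months; 690/30.4375 = 22.7; 750/30.4375 = 24.6.

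If the M24 scan is missing, Period 12.3 likewise has no start scan, and a Gd-negative M36 scan carries the participant event-free to M36.

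**2. Size.** The documents do not give the inputs, so these are assumptions:

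- f, the share with an M48 but no M36 scan: 5–15%
- S, the true 24-month NEDA-3: 60–80%
- h, the share of these participants' events still caught through M48 Gd+, relapse or 6MCDP: 0–50%

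Upward shift = f × (1 − h) × (1 − S).

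| f | h | S | Shift (points) |
|---|---|---|---|
| 0.05 | 0.50 | 0.80 | 0.05 × 0.50 × 0.20 = 0.5 |
| 0.10 | 0.30 | 0.70 | 0.10 × 0.70 × 0.30 = 2.1 |
| 0.15 | 0.00 | 0.60 | 0.15 × 1.00 × 0.40 = 6.0 |

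For scale, the 95% half-width at S = 0.70 is 1.96 × √(0.70 × 0.30/n). This is 6.4 points for n = 200 and 6.1 for n = 220, the evaluable range in Protocol 1.1.

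**3. Remedies, at the middle row (true value 70.0%), with scans missing at random.**

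- Planned rules: 70.0 + 2.1 = 72.1%. A simulated Kaplan-Meier analysis with scans at days 360 and 720 agrees.
- With a Month 24–Month 48 comparison: 70.0%. Year 3 lesions are then dated at M48, so the 12-month estimate is 1 − 0.90 × (1 − √0.70) = 85.3% against a true √0.70 = 83.7%.
- Censoring at the start date without that comparison: if every affected participant leaves, 70.0%. If those with an otherwise detected event keep it and only the event-free leave, the event-free fraction is 0.90 × 0.70 = 0.63, out of 0.90 + 0.10 × 0.30 × 0.30 = 0.909 retained. The estimate is 0.63/0.909 = 69.3%, slightly low.

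The comparison is therefore the better remedy at 24 months, and censoring is for those in whom it cannot be made.

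**The case against.** **Period 48.1 spans the interval.** A reader might infer that T2 change from M24 to M48 is never assessed in these participants. The documents do not support that. If the Baseline to Month 48 count is supplied and is zero, it supports freedom from new or enlarging T2 lesions in the extension. A positive count, however, cannot separate parent-study from extension lesions, and using it as the event would bias NEDA-3 downward. The SAP does not say which Period applies, so the upward direction rests on the natural reading, not an explicit instruction.

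**A fallback may exist elsewhere.** The MRI Periods follow the parent-study analysis plan, version 3.0, and a vendor data specification is cited. Either might set a reference scan when the preceding one is absent. This stands as a limit on the finding, but the visible text contains no such rule.

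**The affected group is narrow.** A reader might infer that missing the M36 scan alone earns 24 months of credit. It does not: an M48 scan, an EDSS near M48 and no other event are all needed, and late M36 scans within the 185-day allowance still count. Nor is MRI activity wholly unassessed, because Gd+ is read at M48. But a single Gd+ reading cannot stand in for T2 change over two years.

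**SAP 9.10.** The plan foresees a time between scans that is missing "due to preceding MRI being missing" and substitutes one year. A reader might infer that this distorts the primary estimate. It does not: the quantity is a model covariate and does not enter the Kaplan-Meier analysis.

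**Exploratory, single-arm design.** No hypothesis is tested, and the likely shift is mostly smaller than the sampling error. Both are true, but on the natural reading the error runs one way and a larger sample would not remove it.

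**Conclusion.** The gap is real and reaches the primary endpoint. No T2 comparison is confined to Month 24–Month 48, and neither the censoring rule nor the descriptive rule in 14.1.1 requires an evaluable active T2 count. The Course 1 and Course 2 definitions do require one, which suggests an oversight. The sensitivity analyses in SAP 14.1.2 do not clearly resolve it: one repeats the primary rules on the treatment completers, one by DMD subgroup, and the crude percentages use the same descriptive rule.

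On the natural reading NEDA-3 is overstated by about 0.5 to 6 points, 2.1 at the middle values. This rests entirely on assumed rates of missing M36 scans and of undetected events. Participants without an M24 scan would add to it; their number is not given. If the parent-study plan supplies a fallback reference scan, the effect could shrink or vanish.

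**What to change.** 1. **Censoring.** In 14.1.1, and in 14.2.1 to 14.2.3 where the wording recurs for NEDA-3, first disease activity and active T2, define the last available MRI as the last extension scan with an evaluable T1 Gd+ count and active T2 counts covering the time from the period's starting reference scan without a break. For time to first active T2 lesion alone, only the T2 condition is needed. If there is no such scan, censor at the start date. This also settles participants with no extension scan, whose last MRI predates the start date.
2. **Periods.** In 9.6 add a Month 24–Month 48 Period, used when M36 is missing or not evaluable. State which reference scan applies when M24 is missing. Allow a zero Period 48.1 count as evidence of T2 freedom, and state that a positive one is not an extension event.
3. **Descriptive rule.** In 14.1.1 require at least one available active T2 value from the extension before MRI activity is called absent, as 14.2.1 does for Course 1 and Course 2.
4. **Reporting.** Give the number of participants lacking an evaluable M24 or M36 scan, and how each was handled.

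**Cost.** Items 1 and 3 are wording. Item 2 needs a few extra central comparisons on existing scans. Some follow-up is lost. Year 3 lesions found on the new comparison are dated at M48, so the 12-month estimate stays slightly high. Where only censoring is possible, the estimate can fall slightly low if otherwise detected events are kept.
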